9.9 Participating sites

This study will be coordinated by two research institutions (sites) in each country and a total of 29 to 37 primary health care clinics (clinics).

Tanzania

- 1. Ifakara Health Institute (IHI)
- 2. National Institute for Medical Research (NIMR/MMRC)

Mozambique

- 1. Centro de investigação de Saúde de Manhiça
- 2. Instituto Nacional de Saúde (INS)

If a primary health care clinic has to stop recruitment during the study, another clinic may be selected to replace that clinic. An additional 8 clinics have been selected as backup clinics, 6 by NIMR-MMRC and 2 by INS.

9.11 Data collection and handling

There will be a maximum of three questionnaires administered per participant: at Visit 1 (baseline; V1-D1 or V1-D1-SE), Visit 2 (Day 7; V2-D7) and Visit 3 (Day 60; V3-D60 or V3-D60-SE). All interviews will be documented on paper CRFs entered electronically, either centrally at the four sites, or at the clinics, into the OpenClinica eCRF/data base located at the LMU. Direct electronic data entry will be supported if a research site has the capacity to do that. The paper CRFs (V1-D1) will be retrieved from clinics on a weekly basis and stored at the central site or entered at the clinic. Data entry of V1-D1 will need to be entered within 6 days of enrolment as it is particularly critical to support the conduct of the V2-D7 phone calls.

V2-D7 and V3-D60 questionnaires will be administered mainly by phone by the research team, entered into the database and filed and stored centrally at the sites. For a subset of participants (approximately 50 per site) a more detailed socio-economic questionnaire (V1-D1-SE) will be conducted at baseline and at the last visit (V3-D60-SE). For those participants the Visit 3 questionnaire may be administered face-to-face.

In addition, details (study-ID, name, sex, age, date of enrolment) of each participant will be documented in a study register, which will stored in a secure location by the site until 10 years after the end of the study unless local regulations or institutional policies require a longer retention period. The study register will be compared with the TB registers and clinic records to ascertain diagnostic results (such as smear results in the standard of care clinics), TB registration number and TB initiation dates. This will be documented on the study TB outcome worksheet. The completed worksheet will be retrieved at the end of the study, entered electronically and stored centrally.

Data on number of contact attempts, contact information provided by trusted proxy, date and location of home visits will be documented on paper in free text. This information will not be entered and stored centrally.

All paper forms (including consent form) will be stored in secure and locked cupboards with only authorised person having access to the forms. The electronic database will not include any names, but only study numbers. The OpenClinica Enterprise version 4.0 database will be secure, password protected and regularly backed-up. Only authorised people will have access to the database.

Truenat TB assay results and error logs will be regularly backed-up on secure FIND servers. Interviews with users will be documented on paper-based questionnaires (user appraisal form). These will be entered into an electronic database.

10.STUDY ASSESSMENTS

10.1 Visit 1:

Demographic and background assessments

Following demographic and background variables will be collected according to the schedule of events table:

- Inclusion and exclusion criteria
- Written informed consent
- Demographic data: date of birth, gender
- Symptoms suggestive of TB
- TB treatment history
- HIV status (including antiretroviral therapy), diabetes
- Smoking and mining history
- Household assets
- Number of visits to a health care provider
- Health care provider first visited
- Costs of care
- Loss of income (SE questionnaire only)

TB investigations and treatment

All participants will be asked to submit a sputum sample for testing using Truenat platform/TB assays (intervention clinics) or standard of care testing (control clinics). TB treatment will be initiated by the clinic team not the study staff.

10.2 Visit 2 and 3 assessments

The following efficacy variables will be assessed for evaluation of efficacy outcomes, at the time points indicated in the schedule of events table and documented on V2-D7 and V3-D60 CRFs.

- TB treatment initiation (at 7 and 60 days from enrolment)
- Microbiological confirmed TB up to 60 days from enrolment from Truenat assay result downloads and study registers

11. PATIENT ENROLMENT

A total of 4200 patients will be enrolled at a minimum of 29 and a maximum of 37 clinics, coordinated by 4 sites in 2 countries, Tanzania and Mozambique. In Mozambique the aim is to recruit 2300 participants (800-1000 recruited by CISM and 1300-1500 by INS). The total number of participants recruited in Mozambique may change dependent on recruitment rates in Tanzania. Tanzania aims to recruit 2100-2600 participants.

Patients will be enrolled into the study only if they meet all the inclusion criteria and none of the exclusion criteria. The unit of randomisation is the clinic; hence patients accessing a certain clinic and consenting to the participate will receive investigations according to the arm into which the clinic was randomised.

11.1 Recruitment procedures

All patients presenting with symptoms suggestive of pulmonary TB will be approached by the primary health care nurses and invited to participate in the study. Posters explaining the study will be placed in the clinics. All materials will be used only upon approval of the ethics committees and/or regulatory authorities relevant for this study.

11.2 Patient informed consent

Patients presenting with signs and symptoms suggestive of pulmonary TB (as per the National Guidelines) will be invited to be screened for inclusion in the study. They will be given a patient information sheet and consent form (ICF) about the study and will be explained the anticipated benefits and the potential risks associated with the protocol procedures. The principal investigator or a person designated by the principal investigator will fully inform the patient. The language used will be as non-technical as possible and the patient will not unduly be influenced to participate in the study. Patients will be told that screening includes asking for symptoms suggestive of pulmonary TB and age. Patients will be told that agreeing to be screened does not mean that they have to join the study, and

Patients will be told that agreeing to be screened does not mean that they have to join the study, and that participation in the study is voluntary. Patients will be informed that they will be free to withdraw from the study at any time, and a withdrawal will have no negative effects on them receiving standard care afterwards.

Written (or witnessed oral informed consent) must be obtained from every patient prior to any procedures being done specifically for the study.

For illiterate patients, study information is given in the presence of an impartial, literate witness, who will read the information sheet to the patient or will witness the complete reading of the information sheet to the patient. The patient will give consent by thumb printing the ICF and the witness states that free, informed consent has been given by his/her signature on the ICF.

The signed original ICF will be kept in a locked cabinet at each research institute. A second original of the signed ICF will be given to the patient or to the patient's legally acceptable representative.

The ICF template will be provided to the investigator by the sponsor. If any modifications to the form are proposed by the site, the consent form must be submitted to the sponsor for approval prior to Protocol short title: TB-CAPT CORE Truenat trial

Protocol Number: TB041-3/1 -MZ

submission to the ethics committee. The ICF will be revised whenever new important information becomes available and will undergo ethics committee review. All active patients must then sign additionally the revised form, after ethics approval was received.

11.3 Incentives and expenses

Participants will not receive any incentives for the participation in the study. For participants who opt to be interviewed and reviewed at the clinics rather than at their homes for the Visit 3, visit transport costs will be reimbursed. The exact amount will be decided by each of the sites.

11.4 Exclusion of particular groups

Children and adolescents aged <18 years will be excluded, because clinical presentation of TB disease differs between children and adults.

11.5 Participant withdrawal

Participant may decide to withdraw from the study at any time and for any reason. The investigator may also withdraw a patient for any of the following reasons:

- Protocol deviation
- If, for any reason, the investigator concludes that continued participation in the study would not be in the participant's best interest

The investigator will also withdraw a patient upon request of the sponsor or if the study is terminated as a whole. Participants who decide to withdraw or who have been withdrawn from the study will not be replaced. After discontinuation of the study participant, the study team will not collect more information for the study but clinical care should continue in the health center. The study will not interfere with treatment; however, it will guarantee adequate referral and assist with screening in the event of loss of follow-up.

12.STUDY PROCEDURES

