9.5.4 Bias reducing measures

The objective of the trial is to assess the Truenat platform/TB assays in clinical care. The use of Truenat platform/TB assays does not allow blinding of clinicians and participants in this trial. The trial-related procedures will be embedded into the routine practice at the primary-level facility. Data analysts will be blinded to intervention allocation.

Randomisation takes place on a cluster level rather than for the individual patients to avoid contamination between the arms within a health facility. Since clinics will be relatively far apart, contamination is unlikely.

We will contact participants for the 7- and 60-day outcomes by telephone to investigate whether more diagnostics available at the level of the primary health care facility (without the need to refer samples) result in more microbiologically confirmed cases and more rapid treatment initiation. Losses to follow-up pre-diagnosis and during treatment are among the endpoints of the trial. There is a chance that contacting the participants after 7 days may influence their treatment seeking behaviour even in the control arm and reduce loss to follow-up. By keeping contact with trial participants to a minimum (i.e., two time points) we hope to limit the impact on treatment seeking behaviour.

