13. STATISTICAL CONSIDERATIONS

13.1 Populations to be analyzed

Intent-to treat (ITT) population: The ITT population will consist of all enrolled patients in the groups to which randomly assigned to intervention and controls. Patients with missing outcome data at days 7 and 60 will be assumed to not have started treatment.

Per-Protocol (PP) population: The PP population will consist of all patients who fulfil the protocol in the terms of eligibility, interventions, and outcome assessment without any major protocol deviation.

The Statistical Analysis Plan (SAP) will define the criteria for the exclusion of patients from any of the above-mentioned analysis populations and will be finalized prior to database lock. The SAP will also provide a detailed summary of the analysis methodology for each of the outcomes of the trial.

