17.2 Safety and incident reporting

The investigator and any qualified designees are responsible for detecting, documenting, and recording events that meet the definition of an adverse events (AE) or severe adverse events (SAE) and remain responsible for following up and reporting AEs that are serious, considered related to the trial intervention or trial procedures, or that caused the participant to discontinue the trial. Given that this is a trial of near patient testing of a WHO endorsed assay (the Truenat platform) the probability of an AE or SAE occurring to a trial participant to be associated with the investigational products is extremely low.

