The investigator will also withdraw a patient upon request of the sponsor or if the study is terminated as a whole. Participants who decide to withdraw or who have been withdrawn from the study will not be replaced. No further follow-up will be conducted after the withdrawal.

Visit 1 Baseline visit

Patients presenting with symptoms suggestive of pulmonary TB to one of the study clinics will be invited to be screened for inclusion in the study. Before any study-specific screening procedures will be performed, all patients will sign and date (or thumbprint) the latest version of the ICF. Illiterate participants will be encouraged to have a witness present.

After informed consent has been obtained, the patient will receive a study number. The ICF will be labelled with the study number. A primary health care nurse or dedicated researcher staff will administer a questionnaire (V1-D1 CRF) and ask the patient about their contact details and the contact details of a trusted proxy (locator form). In addition, a random sample of 5-10% of participants per site will be invited to answer a socio-economic questionnaire about income, cost of care seeking, productivity losses, diagnostics and treatment (V1-D1-SE CRF).

Depending on the clinic, the patient will receive a diagnostic work-up according to the national algorithm (smear microscopy and/or off-site Xpert testing) or the study intervention (Truenat platform/TB assays on site). Further diagnostic investigations and TB treatment initiation will be as clinically indicated. All clinical care and further investigations will be provided within the governmental health care service. Patient details (including name, sex, age and study-ID) will be documented in a study register, which will remain at the clinic. All patients will receive a study card with their details (including name, sex, age and study number and enrolment date) to take home with them. They will be asked to show the card if they present to the clinic again.

Visit 2: Day 7

All participants will be called by telephone 7 days after enrolment (between day 8 and day 21 after enrolment). Three attempts will be made to contact a participant by phone. If these attempts are unsuccessful the trusted proxy will be contacted to find out about the participant's whereabouts and arrange for a return call by the participants or a home visit. A home visit will be conducted for those participants who cannot be reached by phone.

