Results will be reported in both absolute numbers (e.g. number of subjects in a group) and the proportion, or summarized by mean, median, standard deviation, minimum, maximum and quartiles. Differences in the groups of Intervention and SOC will be tested by Chi² Test or Fisher exact test for categorical outcomes, and Kruskal-Wallis test, t- test, ANOVA or Wilcoxon signed rank test for continuous data depending on whether parametric or non-parametric tests are appropriate for the observed data.

QMS Form number: FM-06-02-	CONFIDENTIAL	Page 18 of 26
05/v2.0		-

FIND >>>	Statistical Analysis Plan				
Protocol number:	TB041-3/1-TAN / -MOZ				
Document version:	5.0	Document date:	11-JUL-2023		

6 Additional sub-group analyses

All primary and secondary endpoints will be evaluated separately by sex and gender (if the information is available), HIV status, site, country, asset index, and age categories (as given in Section 5).

7 Exploratory analyses

Protocol Deviation

A proportion of participants were contacted outside of their contact window. 808 participants were affected concerning the V2, and 40 participants were affected concerning the V3. For participants where V2 was not done, V3 was also not done.

Since the data was collected retrospectively, a bias might have occurred since the participants may not recall exactly their status of treatment during the actual Day 7 and Day 60. To overcome this bias.

- 1) A list with IDs of all affected participants was formed by the data manager (15/03/2023 data extract) and reported to national IRB ref: 173/CNBS/23, and this is defined as the MPP population,
- 2) The data that was entered retrospectively was crosschecked with the TB, treatment registry at the clinic (~50 registries) to make sure the treatment initiation data was not misrecorded.
- 3) Descriptive statistics will be performed to describe the number and the percentage of the effected participants (V2, V3, and both) in both arms in the PPM population,
- 4) Descriptive statistics will be performed to describe the number and the percentage of the effected participants for the treatment outcome at day 7. Chi² test will be performed to assess the statistical significance of the difference between the PP and PPM populations. In case of statistical significance, all the models in the study will be adjusted for the deviation (TRUE/FALSE).

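### One stop rule ends data collection after every kind of withdrawal, so outcomes still obtainable from the TB register become failures or exclusions

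*Protocol*

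**What the plan says.** Protocol 11.5 provides three routes out of the study. The participant may leave at any time. The site may act on its own judgement: "The investigator may also withdraw a patient for any of the following reasons", the first listed reason being a protocol deviation, with no severity threshold. The investigator must also withdraw a patient if the sponsor asks. One consequence follows for all three: "After discontinuation of the study participant, the study team will not collect more information for the study". Clinical care and referral continue. SAP 3.1 repeats the grounds and the stop: "No further follow-up will be conducted after the withdrawal".

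Other sections bear on this:

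- **Blinding.** Protocol 9.5.4 says "The use of Truenat platform/TB assays does not allow blinding of clinicians and participants in this trial"; only the data analysts are blinded.
- **Outcome sources.** Protocol 9.8 has a supervisor check the study register against the TB register weekly. Protocol 9.11 takes diagnostic results and treatment-start dates from TB registers and clinic records. Table 1 in 13.5 lists the register and the study TB outcome worksheet, beside the visit 2 call, as sources for the primary endpoint.
- **Missing outcomes.** Protocol 13.1: "Patients with missing outcome data at days 7 and 60 will be assumed to not have started treatment". SAP 4.1 does not impute and analyses the modified ITT and per-protocol sets. SAP 3.2 admits to the modified ITT set only those with visit 2 or visit 3 data.
- **Adverse events.** Under Protocol 17.2 investigators "remain responsible for following up and reporting AEs that are serious", are related to the trial, "or that caused the participant to discontinue the trial".
- **CRFs.** Protocol 14.2 requires a CRF for drop-outs too.

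**The concern.** A stop on data collection protects a participant who no longer consents. When the investigator or sponsor ends participation, consent has not been withdrawn, and the stop gives up data for no stated purpose. Here the outcome does not depend on the participant: the register shows whether TB was confirmed and when treatment began, and study staff already read it.

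The lost outcome is then either scored as a failure (protocol ITT) or removed (SAP modified ITT). The decision to withdraw can be taken after allocation by staff who can know the arm. That staff know the arm is an inference from 9.5.4, which names clinicians rather than investigators as unblinded. What is at stake is complete ascertainment of the primary endpoint, and clear instructions to sites on adverse events and CRFs after discontinuation.

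**Working it through.** **The sections side by side.** Consider a participant withdrawn by the site for a protocol deviation on day 3, who starts treatment for confirmed TB on day 5. The clinic's TB register records the start. The weekly check under 9.8 would find it, but 11.5 and SAP 3.1 say that nothing more is collected. Under 13.1 this success is counted as not started. Under SAP 3.2 and 4.1, with neither visit 2 nor visit 3 data, the participant leaves the modified ITT analysis. If the same withdrawal came after the day-7 outcome had been recorded, the primary endpoint would be unaffected, because nothing says that data already collected are discarded.

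**The plan's own figure.** Inputs from Protocol 13.8, selected scenario: prevalence 12%, sensitivity 89% v 70%, diagnostic loss 2% v 10%, pre-treatment loss 10% v 20%, cluster size 150, CV 0.25, two-sided alpha 0.05, power 80%, A = 1.

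- p_i = 0.12 × 0.89 × 0.98 × 0.90 = 0.0942
- p_c = 0.12 × 0.70 × 0.90 × 0.80 = 0.0605
- Difference = 3.37 percentage points
- Pairs = A + (z_α/2 + z_β)² × V / (p_i − p_c)², where V = p_i(1 − p_i)/150 + p_c(1 − p_c)/150 + 0.25²(p_i² + p_c²)
- Pairs = 1 + 11.95 = 12.95, rounded up to 13, as stated

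SAP section 8 states A = 2, which gives 13.95, rounded up to 14. Its table nevertheless shows 13, so A = 1 is used here.

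**Effect of withdrawals.** For 14 pairs, power = Φ(√[(14 − 1)(p_i − p_c)²/V] − z_α/2). The documents give no withdrawal rate, so the rates w below are assumptions. Withdrawal is taken to precede day-7 ascertainment and to be unrelated to outcome, so scoring as failure multiplies an arm's proportion by (1 − w).

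| Assumed withdrawal, scored as failure | p_i | p_c | Difference (points) | Power |
|---|---|---|---|---|
| None | 9.42% | 6.05% | 3.37 | 83.2% |
| 1% in both arms | 9.33% | 5.99% | 3.34 | 83.0% |
| 5% in both arms | 8.95% | 5.75% | 3.20 | 82.1% |
| 10% in both arms | 8.48% | 5.44% | 3.03 | 80.8% |
| 5%, intervention only | 8.95% | 6.05% | 2.90 | 73.0% |
| 5%, control only | 9.42% | 5.75% | 3.67 | effect inflated |

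Equal withdrawal therefore costs 83.2 − 83.0 = 0.2 to 83.2 − 80.8 = 2.4 power points. If 10% in each arm are excluded instead, cluster size falls to 135, the expected difference stays at 3.37 and power is 81.0%.

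**The case against.** **What stands.** Withdrawal by the site is discretionary. The window for harm to the primary endpoint is short: before day 8 the only scheduled contact is visit 1, the intervention aims at same-day treatment, and registers are checked weekly. Major deviations already have a route through the per-protocol definition. These points limit the size of the problem but do not give the stop a purpose when consent has not been withdrawn.

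**Stronger readings that a reader might infer, and why they fail:**

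- *That the reported deviations show how many could be lost.* SAP section 7 says "808 participants were affected concerning the V2", which is 808/4200 = 19.2% of the planned sample. These participants were contacted outside the window. Their data were collected late and cross-checked against the clinic treatment registry, and the SAP gives them a named analysis population. That points to keeping them, not withdrawing them.
- *That the rule favours one arm.* With 2100 per arm, about 198 v 127 successes are planned, so 1% withdrawn costs about 2.0 v 1.3. That gap reflects only the different base rates; equal percentage loss leaves the ratio unchanged. A platform failure could occur only in the intervention arm, but no section classes it as a deviation or a reason for withdrawal; it is a planned operational endpoint.
- *That a site cannot obey both 11.5 and 17.2.* Section 17.2 can be read as a specific exception to a general stop on study information, and it expressly keeps the adverse-event duty. Neither document states that reading, so the sections are unreconciled but not impossible to follow together. Protocol 17.2 also judges device-related events extremely unlikely.

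**Conclusion.** The concern holds for the scope of the stop rule. Protocol 11.5 and SAP 3.1 apply to investigator- and sponsor-initiated withdrawal a restriction that is needed only for withdrawn consent. Followed as written, obtainable primary-outcome data are turned into failures or exclusions whenever such a withdrawal precedes day-7 ascertainment. The rule also needs reconciling with Protocol 17.2 and 14.2.

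The size is unknown because no withdrawal rate is given. Under the assumptions above, equal loss is minor. Only loss that differs between arms would shift the estimate materially, and the documents contain no evidence of it. The point should be corrected because the rule brings no benefit outside withdrawn consent and is cheap to narrow, not because bias has been shown.

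**What to change.** In Protocol 11.5 and SAP 3.1:

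1. Remove protocol deviation as a ground for withdrawal. Record the deviation, keep the participant in follow-up, and handle it through the per-protocol definition.
2. State that withdrawal ends study contacts, but that confirmation and treatment-start dates from the register and worksheet continue to be recorded unless the participant withdraws consent to use of records. Vital status should not be added to this list without checking its source: Protocol 14.3 treats it as CRF data.
3. Reconcile 11.5 with 17.2 on adverse events and with 14.2 on CRF completion, so that sites know what continues after discontinuation.
4. For participants already withdrawn by the investigator or sponsor, complete outcomes from the registers only where consent and ethics approval allow. The consent form was not available for this review, so this cannot be assumed. Report withdrawals by arm, initiator and reason.

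The cost is a protocol amendment, matching SAP text and possibly consent-form wording. A few participants with recorded deviations will stay in the analysis. The weekly register check already exists, so no new field procedure is needed.
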